6.3.2. Other Safety Summaries and Analyses Endpoint(s)

6.3.2.1. Laboratory Data

In general, no local laboratory assessments will be used in any summaries except for lipid panel and thyroid panel tests. No local laboratory assessments will be used to derive maximum/minimum/worst value unless specified otherwise. Local laboratory assessments will be listed.

For the sites and/or countries where central laboratory assessments are not available (due to reason such as war in Ukraine) and local laboratory assessments are collected, the local laboratory assessments could be considered for laboratory related analyses, if deemed appropriate.

Safety Laboratory Evaluations

Hematology, serum chemistry, coagulation, and urinalysis will be analyzed and reported by central laboratory and sometimes by local laboratory. Results out of reference range are flagged by the performing laboratory (eg, low, high). A full list of laboratory assessments to be included in the outputs is included in Table 5 ("Clinical Laboratory Tests") of Clinical Study Protocol C5041011 (APD334-210) amendment 2.0.

In general, presentations will use SI units. Quantitative laboratory measurements reported as "< X" or "> X", where X may be the lower limit of quantitation (LLQ) or the upper limit of quantitation (ULQ), respectively, will be converted to X for the purpose of quantitative

summaries, but will be presented as recorded, ie, as "< X" or "> X" in the listings. For urinalysis, only pH and specific gravity are considered as quantitative tests. If local and central laboratory assessments are available from the same day, central laboratory assessments will be used in the summary as per Section 9.1.4.

The following summaries will be provided for laboratory data:

- Value and change from Baseline by visit (e.g., hematology, serum chemistry, and coagulation)
- Incidence of markedly abnormal lymphocytes and neutrophils at anytime post-baseline, End of Treatment, any Follow up.
 - O Markedly Abnormal lymphocytes and neutrophil is defined as Lymphocytes $< 0.2 \times 10^9/L$, $0.5 \times 10^9/L$, or Neutrophils $< 0.5 \times 10^9/L$, $1 \times 10^9/L$.
- Shift from end of treatment to each follow-up visit in incidence of lymphocytes for participants with abnormal low value at end of treatment.
- Evaluation of drug-induced serious hepatotoxicity (eDISH) plots for the following laboratory assessments (using values after the first administration of study treatment):
 - Maximum aspartate aminotransferase (AST) versus same-day total bilirubin
 - Maximum alanine aminotransferase (ALT) versus same-day total bilirubin

The eDISH plots above will be repeated with adjustment for elevated Baseline.

- Incidence of hepatic enzyme elevations by visit and overall post baseline
 - $> 1 \times, 2 \times, 3 \times, 5 \times, 8 \times, 10 \times, 20 \times$ upper limit of normal (ULN) elevation in ALT
 - \rightarrow 1 ×, 2 ×, 3 ×, 5 ×, 8 ×, 10 ×, 20 × ULN elevation in AST
 - $> 3 \times, 5 \times, 10 \times, 20 \times$ ULN elevation in either ALT or AST
 - \rightarrow 1 ×, 1.5 ×, 2 ×, 3 × ULN elevation in total bilirubin
 - \rightarrow 1 ×, 1.5 ×, 2 ×, 3 ×, 5 ×, 8 × ULN elevation in ALP
 - $\rightarrow 1 \times, 2 \times, 3 \times, 5 \times, 8 \times \text{ULN elevation in GGT}$
 - $> 3 \times ULN$ elevation in either ALT or AST and $> 1.5 \times ULN$ elevation in total
 - bilirubin
 - $> 3 \times ULN$ elevation in either ALT or AST and $> 2 \times ULN$ elevation in total
 - bilirubin

- $> 3 \times \text{ULN}$ elevation in either ALT or AST and $> 1.5 \times \text{ULN}$ elevation in ALP
- \sim 3 × ULN elevation in either ALT or AST in temporal association with

treatment-emergent nausea, vomiting, anorexia, abdominal pain, or fatigue identified by PT, where temporal association is defined as ± 14 days of onset date from the time of elevation.

If both central and local assessments of total bilirubin are available on the same day, the central result will take precedence over the local result in the eDISH plot. If the maximum AST, ALT, GGT, or ALP assessment occurs at 2 different dates, the assessment with the higher accompanying Bilirubin value will be used. Two versions of the eDISH plots will be presented, with one showing values as multiples of ULN, and the other one showing values as multiples of ULN, or participant's baseline, whichever is higher.

Participant's laboratory assessments at all timepoints will be listed in chronological order. Values outside of the laboratory reference range will be flagged. Values obtained from local laboratory will be flagged. A listing of lymphocytes and neutrophils over time in participants who ever had lymphocytes $< 0.5 \times 10^9/L$ or neutrophils $< 1 \times 10^9/L$ will also be provided.

Pregnancy Tests

Pregnancy tests are performed throughout the study (Serum β-hCG test at Screening; urine pregnancy test at all other visits) in female participants of childbearing potential. All pregnancy test results (positive or negative) will be listed in chronological order. Number of female participants with positive urine/serum pregnancy test will be summarized.

Other Screening Laboratory Assessments

Other screening laboratory assessments conducted per Table 5 ("Clinical Laboratory Tests") of Protocol C5041011(APD334-210) amendment 2.0 will be listed.

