9.9.8. Clinical Laboratory Tests

Refer to Table 5 for the list of clinical laboratory tests to be performed and the Schedule of Assessments (Appendix 1, Table 6) for timing and frequency for each test. Details regarding clinical laboratory sample collection, preparation, and shipment are provided in the Laboratory Manual by the central laboratory.

Clinical safety laboratory tests should be completed pre-dose. The Investigator must review the laboratory report, document this review, and record any clinically relevant changes occurring

during the study in the adverse event section of the eCRF. Results of the total WBC and ALC will be reviewed and monitored as described in Section 9.8.5. The laboratory reports must be filed with the source documents. Clinically significant abnormal laboratory findings are those that are not associated with the underlying disease, unless judged by the Investigator to be more severe than expected for the subject's condition.

All laboratory tests with values considered clinically significantly abnormal during participation in the study or within 30 days after the last administration of study treatment should be repeated until the values return to normal or baseline or are no longer considered clinically significant by the Investigator or Medical Monitor.

- If such values do not return to normal/baseline within a period of time judged reasonable by the Investigator, the etiology should be identified, and the Sponsor should be notified.
- All protocol-required laboratory assessments, as defined in the Schedule of Assessments (Appendix 1, Table 6), must be conducted in accordance with the Laboratory Manual.
- If laboratory values from non-protocol-specified laboratory assessments performed at the institution's local laboratory require a change in subject management or are considered clinically significant by the Investigator (eg, adverse event, SAE, or dose modification), then the results must be recorded in the eCRF.

For guidance on monitoring subjects with notable lymphopenia, refer to Section 9.8.5.

Table 5: Clinical Laboratory Tests

SCREENING ONLY

Virology

HIV, HBsAg, HCV (RIBA)

Stool Sample

Bacterial culture, ova and parasites, C. difficile

Drugs of Abuse

Amphetamine, barbiturates, benzodiazepines, cocaine, methadone,

methamphetamine, methylenedioxymethamphetamine, opiate, oxycodone,

phencyclidine

Others

Hemoglobin A1C, QuantiFERON

PREGNANCY TESTING

Serum pregnancy test β-hCG - Screening

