9.1.3. Retests, Unscheduled Visits, and Early Termination Data

For by-visit analyses and summaries, efficacy, safety, HRQoL, and biomarker data (including scheduled, retests, unscheduled, and early termination) will be assigned to visits after the application of the windowing conventions described in Section 9.1.4 below. All measurements will be considered in summaries of abnormalities or worst-case values post-Baseline. The visit windowing will be applied before missing data are imputed. Listings will include scheduled, unscheduled, retest, and early termination data.

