If two or more measurements for an endpoint fall in a same analysis visit window, the measurement with the date closest to the protocol scheduled visit day will be used in the analysis. If 2 measurements in the same analysis visit window are equidistant from the protocol scheduled visit day, the earlier one will be used in the analysis. If multiple measurements are available on the same day, then the average of the measurements will be used in the analysis, except for laboratory and ECG data where the assessment at the earliest time of the same day will be used. If both central and local assessments of the same ECG or lab test are available on the same day, the central result will take precedence over the local result.

For the overlapping visit windows at Week 12 and Week 8/16, a hierarchical algorithm will be applied as follows: always map to the Week 12 study visit if the study day falls within the visit window of the Week 12 study visit, then assess the other records for the Week 8 or Week 16 study visit. The same algorithm will be used for Week 48 and Week 52, with Week 52 taking priority.

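### Liver-enzyme peaks measured only at a local laboratory are left out of the hepatic threshold rows and eDISH maxima, and no supplementary version restores them

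*SAP*

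**What the plan says.** SAP 6.3.2.1 sets two defaults. Local results enter no laboratory summaries apart from the lipid and thyroid panels. For extremes it adds: "No local laboratory assessments will be used to derive maximum/minimum/worst value unless specified otherwise". Local results are listed, with their source flagged.

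Three rules give central results priority over local ones, all on a same-day basis:

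- General laboratory summaries (SAP 6.3.2.1): "If local and central laboratory assessments are available from the same day, central laboratory assessments will be used in the summary".
- The eDISH plot (SAP 6.3.2.1): "If both central and local assessments of total bilirubin are available on the same day, the central result will take precedence".
- Visit windows (SAP 9.1.4): central prevails "If both central and local assessments of the same ECG or lab test are available on the same day".

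For sites or countries without central testing, SAP 6.3.2.1 says that "the local laboratory assessments could be considered for laboratory related analyses, if deemed appropriate". SAP 9.1.3, which deals with retests, unscheduled visits and early termination, says: "All measurements will be considered in summaries of abnormalities or worst-case values post-Baseline".

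Protocol 9.1 makes the central laboratory the normal source of protocol-required tests. Protocol 9.9.8 requires an eCRF entry when "laboratory values from non-protocol-specified laboratory assessments performed at the institution's local laboratory require a change in subject management or are considered clinically significant". Protocol 5.1 makes ALT or AST above 8 × ULN a mandatory reason to stop study treatment.

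**The concern.** The overall post-baseline hepatic rows and the eDISH plots exist to show the worst value each subject reached. The local results that Protocol 9.9.8 brings into the database are, by construction, those that changed management or were judged clinically significant. A default that removes them from the extremes removes values that are more likely than average to be the extreme.

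What is at stake is how completely the descriptive liver outputs show severity. A subject whose true peak was local and whose later central repeat was lower would appear in a milder threshold row or at a milder eDISH point, or would be missing from a row. A reader of the tables and plots would have to go to the listings to find out.

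**Working it through.** The plan gives no figure on this point to reproduce. The check is a reading of the rules together, a count of outputs, and a scale illustration.

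**1. Following one subject through the rules.** Suppose a local ALT is above 8 × ULN, there is no central sample that day, and the later central repeat lies between 3 and 5 × ULN.

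- Protocol 5.1: treatment must stop.
- Protocol 9.9.8: the local value goes into the eCRF.
- SAP 6.3.2.1: the local value is listed and flagged but cannot be the maximum.
- Result: the subject counts in the ALT rows for > 1, > 2 and > 3 × ULN, but not in > 5 or > 8 × ULN, and the eDISH maximum is the central repeat.

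The same-day rules do not alter this, because there is no same-day central result.

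**2. Whether the precedence rules fit the default.** The general and visit-window rules can be explained by the lipid and thyroid exceptions, and the visit-window rule also covers ECGs, which are read both locally and centrally. The bilirubin rule cannot be explained in this way. If local bilirubin were never eligible, giving central bilirubin precedence in the eDISH plot would have no effect. The provision for sites without central testing hardly explains it either, since a same-day conflict needs a central result. The natural reading is that a local bilirubin may be plotted when it stands alone. No matching sentence covers ALT or AST, so from a single local draw the bilirubin appears eligible and the enzymes do not.

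**3. Whether SAP 9.1.3 settles it.** Its sentence on all measurements concerns visit type (scheduled, retest, unscheduled, early termination). It does not mention laboratory source and can be applied alongside 6.3.2.1, so it does not override the exclusion.

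**4. Outputs concerned, counted from SAP 6.3.2.1.**

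| Group | Rows |
|---|---|
| ALT | 7 |
| AST | 7 |
| ALT or AST | 4 |
| Total bilirubin | 4 |
| ALP | 6 |
| GGT | 5 |
| Combined criteria | 4 |
| **Total** | **37** |

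eDISH: 2 enzymes × 2 versions (multiples of ULN; multiples of ULN or baseline, whichever is higher) = 4 plots.

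**5. Scale.** The documents do not give the frequency of local-only peaks. Assumption: the planned 150 etrasimod and 75 placebo subjects are all treated. One subject is 1/150 = 0.67 points or 1/75 = 1.33 points. For a row that otherwise shows no cases, the Clopper-Pearson 95% intervals are as follows (with zero cases the upper limit is 1 − 0.025^(1/n)):

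| Local-only cases added | Etrasimod (n = 150) | Placebo (n = 75) |
|---|---|---|
| 0 | 0% (0 to 2.43) | 0% (0 to 4.80) |
| 1 | 0.67% (0.02 to 3.66) | 1.33% (0.03 to 7.21) |
| 2 | 1.33% (0.16 to 4.73) | 2.67% (0.32 to 9.30) |
| 3 | 2.00% (0.41 to 5.73) | 4.00% (0.83 to 11.25) |

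The case counts are illustrative. If local-only extremes occurred in 0.5% to 2% of subjects (also an assumption), 225 × 0.005 = 1.1 to 225 × 0.02 = 4.5 subjects would be involved.

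**The case against.** The strongest reply is that the SAP made a deliberate and defensible choice. Assays differ between laboratories, and local results are captured selectively because of what they show. That stands, and it is why central-only should remain primary. It also follows that the SAP is not silent. A reader might infer from the same-day rules that a local-only peak is unaddressed, but the default in 6.3.2.1 does address it, by excluding it from the maxima and listing it.

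A reader might also infer that a liver signal could disappear. The documents do not support that:

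- Protocol Appendix 6 recalls subjects with potential Hy's Law values, preferably within 48 hours, and cases confirmed on repeat with no other cause found are reported as SAEs.
- Protocol 9.9.8 has clinically significant values repeated until they settle, and Protocol 5.1 asks for an early termination visit.
- Liver injury is a special-interest category (SAP 3.2.2.1), liver-related discontinuations and deaths are summarised (SAP 6.3.1.5), and all values are listed.

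These safeguards stand, but none feeds the threshold rows or the eDISH plots.

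A third tempting inference is that lymphocyte and neutrophil nadirs are equally exposed. They are not. Protocol-required counts are central, investigators are blinded to them during treatment and follow-up (Protocol 9.8.5), and they are scheduled at nearly every on-treatment visit. The one CBC explicitly left to local standard of care comes after the 4-Week Follow-Up (Protocol 9.5).

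Finally, the eDISH inconsistency may rarely matter, because ALT, AST and bilirubin sit in the same chemistry panel. That limits its practical effect but does not settle which rule a programmer should follow.

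**Conclusion.** The concern holds for liver tests, at minor severity. By default, a local-only ALT or AST peak is absent from the overall post-baseline hepatic rows and the eDISH maxima, and the eDISH text treats local bilirubin and local enzymes differently without saying so. For sites without central testing, eligibility is left to judgement with no stated criterion.

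Up to 37 rows and 4 plots are open to this. That is a count of planned outputs, not of outputs known to be wrong. The number of subjects cannot be derived from the documents and is probably small. The illustrative intervals overlap, and these are descriptive summaries without hypothesis tests, so nothing suggests a changed statistical conclusion. Efficacy, power and type I error are untouched.

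The verdict rests on reading the bilirubin precedence rule as having some effect, and on some clinically significant local liver results being recorded on days without a central sample.

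**What to change.** Keep the central-only outputs as primary. Before unblinding, prespecify one supplementary version of the overall post-baseline hepatic threshold and combined rows and of the eDISH plots:

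- Add local ALT, AST, ALP, GGT and total bilirubin when no same-day central result exists.
- Scale each value to the performing laboratory's ULN.
- Flag local-only cases. Leave values lacking a ULN in the listing and footnote their number.

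Also state in the eDISH text that local ALT/AST and local bilirubin are treated alike, and replace the discretionary wording for sites without central testing with a rule that their local liver results enter this version. A short sentence in SAP 9.1.3 pointing to 6.3.2.1 for eligibility by laboratory source would remove the remaining ambiguity. Extending the version to lymphocyte and neutrophil nadirs is optional, since ULN scaling does not apply to absolute counts.

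The cost is a few SAP sentences, a source flag and one extra run of existing programs. No new data are needed if local ULNs are recorded. The SAP says the performing laboratory flags out-of-range results, but the documents do not say that the numeric limit is collected. The drawbacks are inter-laboratory differences and selective capture, which is why this version should be supplementary.

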5. REMOVAL OF SUBJECTS FROM STUDY TREATMENT OR ASSESSMENT

5.1. Discontinuation from Study Treatment

A subject's double-blind treatment may be discontinued for any of the following reasons:

- Worsening of disease (Note: If a subject discontinues double-blind treatment at any time starting with the Week 12 assessment, the subject may be eligible to enter the APD334-303 OLE study [Section 5.1.1])
- Adverse event that in the judgement of the Investigator and/or Medical Monitor the subject should not continue study treatment
- Subject noncompliance with the protocol or study treatment that is considered significant by the Medical Monitor
- Investigator decision
- Withdrawal by subject or parent/guardian (if applicable)
- Lack of efficacy
- Lost to follow-up
- Study termination by Sponsor
- Other, non-adverse event

A subject's double-blind treatment must be discontinued for any of the following reasons:

- Decline in PFT values (FEV₁ and/or FVC) below 50% of the predicted values
- Confirmed diagnosis of clinically significant macular edema
- Confirmed diagnosis of active TB
- Subjects who have a cardiovascular treatment-related symptomatic event (eg, chest pain, dizziness, palpitations, lightheadedness, shortness of breath, or syncope) associated with reduction of the heart rate or associated with clinically relevant ECG changes at any time during the 4-hour monitoring period on Day 1 or Day 2 (as applicable) (Section 9.4.2.1)
- Subjects who have not met the discharge criteria on Day 1 after ≥ 4 hours of extended monitoring, or Day 2 by 4 hours post-dose (Table 3).
- Pregnancy (Section 9.9.10)
- Suspected drug induced liver injury as defined by the 2009 FDA Guidance for Industry (FDA 2009)

- ALT or AST > 8 × ULN
- ALT or AST > 5 × ULN for > 2 weeks
- ALT or AST > 3 × ULN and (total bilirubin > 2 × ULN or international normalized ratio > 1.5)
- ALT or AST > 3 × ULN with the appearance of fatigue, nausea, vomiting, right upper quadrant pain or tenderness, fever, rash, and/or eosinophilia (> 5%)

Because transient fluctuations of ALT or AST are common, and progression to severe drug-induced liver injury or acute liver failure is uncommon, automatic discontinuation of study treatment upon finding a greater than 3 × ULN elevation of ALT or AST may be unnecessary. If a drug-induced liver injury is identified, refer to Appendix 6 for guidance.

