16. APPENDICES

APPENDIX 1: SCHEDULE OF ASSESSMENTS

Table 6: Schedule of Assessments

Evaluation	Screening		12-Week Treatment Perioda					40-Week Treatment Period ^a						
	-28 to -1	W0/ D1	W2/ D15 ± 3	W4/ D29 ± 3	W8/ D57 ± 3	W12/ D85 ± 3 ^b	W16/ D113 ± 7	W24/ D169 ± 7	W32/ D225 ± 7	W40/ D281 ± 7 (virtual)	W48/ D337 ± 7	W52/D 365/ ET ± 7 ^b	2W F/U ± 3°	4W F/U ± 3°
Informed consent	X													
Inclusion/exclusion criteria	X	X												
Demographics	X													
Medical and social historyd	X													
Ulcerative colitis history	X													
Chest X-raye	X													
Tuberculosis test ^f	X											X		
Tuberculosis questionnaire ^f	X	X	X	X	X	X	X	X	X	X	X	X	X	X
Virology screen (HIV, HBV, HCV) ^g	Х													
Randomization		X												
eDiary instructionh	X													
eDiary review		X	X	X	X	X	X	X	X	X	X	X		
PGAi		X				X						X		
MMS/TMS ^j		X				X						X		
Stool frequency and rectal bleeding subscores ^k		Х	X	X	X	X	X	Х	Х	Х	X	X		

Evaluation	Screening	12-Week Treatment Perioda 40-Week Treatment Peri			iod ^a									
	−28 to −1	W0/ D1	W2/ D15 ± 3	W4/ D29 ± 3	W8/ D57 ± 3	W12/ D85 ± 3 ^b	W16/ D113 ± 7	W24/ D169 ± 7	W32/ D225 ± 7	W40/ D281 ± 7 (virtual)	W48/ D337 ± 7	W52/D 365/ ET ± 7 ^b	2W F/U ± 3c	4W F/U ± 3°
IBDQ, UC-PRO ¹ , SF-36, WPAI-UC, FACIT-F, urgency NRS, and PGIC		X				Х			Xm			X		
Adverse event assessment	+												-	
Vital signs ⁿ	X ⁿ	Xn,o	X	X	X	X	X	X	X		X	X	X	X
12-lead ECG ^p	$\mathbf{X}^{\mathbf{q}}$	$\mathbf{X}^{\mathbf{p},\mathbf{q}}$				X						X		
Holter monitor ^r		X												
Physical examinations	X	X	X	X	X	X	X	X	X		X	X	X	X
Extraintestinal manifestations ^t	X					X						X	X	X
Pulmonary function test ^u	Xv					X			X			X	X	
Ophthalmoscopy with OCTw	X					X						X	X	
Urine drug screen ^x	X													
Pregnancy test ^y	X	X		X	X	X	X	X	X	X	X	X		X
CBC with differential and platelets ^z	X	X	X	X	X	X	X	X	X		X	X	X	X
CCI	X	X	X	X	X	X	X	X	X		X	X	X	X
Laboratory tests including hs-CRP ^{aa}	X	X	X	X	X	X	X	X	X		X	X	X	
Stool sample/fecal calprotectin ^{bb}	X		X	X	X	X		X				X		
CCI	X					X						X		
Endoscopy and biopsy (histologic indices) ^{cc}	X					X						X		

090177e1a2002994\Approved\Approved On: 23-Oct-2024 03:11 (GMT)

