APPENDIX 6: LIVER SAFETY: SUGGESTED ACTIONS AND FOLLOW-UP ASSESSMENTS

Potential Cases of Drug-Induced Liver Injury

Humans exposed to a drug who show no sign of liver injury (as determined by elevations in transaminases) are termed "tolerators," while those who show transient liver injury but adapt are termed "adaptors." In some subjects, transaminase elevations are a harbinger of a more serious potential outcome. These subjects fail to adapt and therefore are "susceptible" to progressive and serious liver injury, commonly referred to as a drug induced liver injury (DILI). Subjects who experience a transaminase elevation above 3 × upper limit of normal (ULN) should be monitored more frequently to determine if they are "adaptors" or are "susceptible."

In the majority of DILI cases, elevations in aspartate aminotransferase (AST) and/or alanine aminotransferase (ALT) precede total bilirubin elevations (> 2 × ULN) by several days or weeks. The increase in total bilirubin typically occurs while AST/ALT is/are still elevated above 3 × ULN (ie, AST/ALT and total bilirubin values will be elevated within the same laboratory sample). In rare instances, by the time total bilirubin elevations are detected, AST/ALT values might have decreased. This occurrence is still regarded as a potential DILI. Therefore, abnormal elevations in either AST or ALT in addition to total bilirubin that meet the criteria outlined below are considered potential DILI (assessed per Hy's Law criteria) cases and should always be considered important medical events, even before all other possible causes of liver injury have been excluded.

The threshold of laboratory abnormalities for a potential DILI case depends on the subject's individual baseline values and underlying conditions. Subjects who present with the following laboratory abnormalities should be evaluated further as potential DILI (Hy's Law) cases to definitively determine the etiology of the abnormal laboratory values:

- Subjects with AST/ALT and total bilirubin baseline values within the normal range who subsequently present with AST or ALT values ≥ 3 × ULN and a total bilirubin value ≥ 2 × ULN with no evidence of hemolysis and an alkaline phosphatase value < 2 × ULN or not available.
- For subjects with baseline AST or ALT or total bilirubin values above the ULN, the following threshold values are used in the definition mentioned above, as needed, depending on which values are above the ULN at baseline:

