 - Preexisting AST or ALT baseline values above the normal range: AST or ALT values ≥ 2 times the baseline values and ≥ 3 × ULN; or ≥ 8 × ULN (whichever is smaller).
 - Preexisting values of total bilirubin above the normal range: total bilirubin level increased from baseline value by an amount of ≥ 1 × ULN or if the value reaches ≥ 3 × ULN (whichever is smaller).

Rises in AST/ALT and total bilirubin separated by more than a few weeks should be assessed individually based on clinical judgment; any case where uncertainty remains as to whether it represents a potential Hy's Law case should be reviewed with the Sponsor.

The subjects should return to the investigator site and be evaluated as soon as possible, preferably within 48 hours from awareness of the abnormal results. This evaluation should include laboratory tests, detailed history, and physical assessment.

In addition to repeating measurements of AST and ALT and total bilirubin for suspected Hy's Law cases, additional laboratory tests should include albumin, creatine kinase (CK), direct and indirect bilirubin, gamma-glutamyl transferase (GGT), prothrombin time/international normalized ratio (PT/INR), total bile acids, and alkaline phosphatase. Consideration should also be given to drawing a separate tube of clotted blood and an anticoagulated tube of blood for further testing, as needed, for further contemporaneous analyses at the time of the recognized initial abnormalities to determine etiology. A detailed history, including relevant information, such as review of ethanol, acetaminophen/paracetamol (either by itself or as a coformulated product in prescription or over-the-counter medications), recreational drug, or supplement (herbal) use and consumption, family history, sexual history, travel history, history of contact with a jaundiced person, surgery, blood transfusion, history of liver or allergic disease, and potential occupational exposure to chemicals, should be collected. Further testing for acute hepatitis A, B, C, D, and E infection, liver imaging (eg, biliary tract), and collection of serum samples for acetaminophen/paracetamol drug and/or protein adduct levels may be warranted.

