All cases demonstrated on repeat testing as meeting the laboratory criteria of AST/ALT and total bilirubin elevation defined above should be considered potential DILI (Hy's Law) cases if no other reason for the liver function test (LFT) abnormalities has yet been found. Such potential DILI (Hy's Law) cases are to be reported as serious adverse events (SAEs), irrespective of availability of all the results of the investigations performed to determine etiology of the LFT abnormalities.

A potential DILI (Hy's Law) case becomes a confirmed case only after all results of reasonable investigations have been received and have excluded an alternative etiology.

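### The SAP counts uncorrected QT above 500 ms but not QTcF above 500 ms, the level at which the protocol acts (minor, descriptive displays only)

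*SAP*

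**What the plan says.** **ECG.** SAP 6.3.2.2 sets two absolute levels: QTcF of at least 450 ms (men) or 470 ms (women), and QT above 500 ms. It adds increases from baseline of more than 30 ms and more than 60 ms, for both QT and QTcF. There is no absolute QTcF level above 450/470 ms. Protocol 9.9.3 asks for a repeat ECG when a new QTc above 500 ms appears and for interruption of treatment if it is confirmed. That section does not name the correction at the 500 ms threshold. However, QTcF is the only corrected interval it lists for the read, and it states its condition for restarting treatment in QTcF.

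**Liver.** SAP 6.3.2.1 plots "Maximum alanine aminotransferase (ALT) versus same-day total bilirubin", with the same pairing for AST. If the peak falls on two dates, the date with the higher bilirubin is used. The same section tabulates ALT or AST above 3 × ULN together with bilirubin above 2 × ULN, by visit and overall after baseline. Protocol Appendix 6 says that in most cases of drug-induced liver injury the enzyme elevations "precede total bilirubin elevations (> 2 × ULN) by several days or weeks". It goes on to say that ALT/AST is typically still above 3 × ULN in the same sample when bilirubin rises. It describes an earlier fall in ALT/AST as rare, though still a potential case.

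**The concern.** A reader of the safety tables will want to know how many participants in each arm passed the protocol's own ECG threshold. The QT row looks like that count but is not, because uncorrected QT depends on heart rate. The QTcF row that does exist counts a man at 451 ms and a man at 520 ms alike. What is at stake is how directly the tables answer that question, not whether the data exist.

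The liver point is of the same kind and weaker. A plot tied to the day of the enzyme peak cannot show a bilirubin rise that comes later.

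**Working it through.** The plan gives no figure to reproduce, so the check compares definitions and converts QT to QTcF.

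**ECG inputs.** The 500 ms level and the interval it applies to come from SAP 6.3.2.2 and Protocol 9.9.3. The Fridericia formula is an assumption: the documents name the correction but do not print it. The heart rates are illustrative.

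Formula: QTcF = QT / RR^(1/3) with RR = 60/HR in seconds, so QTcF = QT × (HR/60)^(1/3). The QT at which QTcF equals 500 ms is 500 × (60/HR)^(1/3).

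| Heart rate (bpm) | QTcF when QT = 500 ms | QT at which QTcF = 500 ms |
|---|---|---|
| 50 | 470.5 | 531.3 |
| 60 | 500.0 | 500.0 |
| 75 | 538.6 | 464.2 |
| 80 | 550.3 | 454.3 |
| 100 | 592.8 | 421.7 |

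Above 60 bpm the QT row misses participants over the protocol threshold. At 75 bpm these are QT values of 465 to 500 ms, or QTcF of about 501 to 539 ms. Below 60 bpm the row can flag participants who are under the threshold.

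**What already exposes a QTcF above 500 ms.**
- It also exceeds 450/470 ms, so the participant is counted in that row and all of that participant's QTcF values are listed (SAP 6.3.2.2). Listings are sorted by treatment group (SAP 9.4).
- Eligibility keeps baseline QTcF below 450 ms in men and at no more than about 470 ms in women (Protocol 4.2 and 9.4.1). An eligible participant above 500 ms has therefore risen by more than 500 − 450 = 50 ms (men) or 500 − 470 = 30 ms (women), and is also in the row for increases above 30 ms.
- QTcF is summarized by visit (SAP 6.3.2.2), and descriptive summaries of continuous variables include the maximum (SAP 5.2). A value above 500 ms shows there if it is the one selected for that analysis visit.

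Only the count by arm at the protocol's threshold is missing.

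**Liver.** The SAP draws no quadrant lines, so I use the pair in Protocol 5.1, "ALT or AST > 3 × ULN and (total bilirubin > 2 × ULN". The laboratory values below are invented for illustration, in multiples of ULN.
- Case A: ALT 6 and bilirubin 1 at Week 4, then ALT 4 and bilirubin 2.5 at Week 8. The plotted point is (6, 1), outside the quadrant. The by-visit combined row counts Week 8, since 4 > 3 and 2.5 > 2.
- Case B: the same, but with ALT 2.5 at Week 8. Neither the plot nor the by-visit row shows it. The overall row shows it only if the two values may come from different samples, which SAP 6.3.2.1 does not say.

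Case A is the course Appendix 6 calls typical and case B the one it calls rare. The tie rule helps in neither, because the peak occurs once.

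**The case against.** The strongest reply is that this is preference, not defect. The protocol asks for neither a QTcF > 500 ms table nor a particular eDISH pairing. Protocol 9.9.3 is an instruction to sites, and the safety endpoints in Protocol 10.11.1 name no ECG measure. That stands as far as it goes: nothing in the SAP contradicts the protocol. It does not explain why the one 500 ms row uses the interval that does not match the protocol's threshold, when the matching interval is on the same read.

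On the liver side the reply is stronger. A reader might infer from "precede total bilirubin elevations (> 2 × ULN) by several days or weeks" that the same-day rule hides the usual course of a Hy's Law case. The documents do not support that, because the rest of the Appendix 6 paragraph puts the usual case in the combined row. Other safeguards also stand:
- Potential Hy's Law cases "are to be reported as serious adverse events (SAEs), irrespective of availability of all the results", so they reach the serious TEAE summaries (SAP 6.3.1.3).
- Liver injury is a special-interest category compared between arms (SAP 3.2.2.1, 6.3.1.4 and 6.3.1.5).
- All laboratory values are listed in date order (SAP 6.3.2.1).

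A reader might also treat visit spacing as a measure of the problem. After the first dose, scheduled chemistry ("Laboratory tests including hs-CRP" in Protocol Table 6) falls on Days 15, 29, 57, 85, 113, 169, 225, 337 and 365, with gaps of 14 to 112 days. Those gaps do not describe the participants concerned. Appendix 6 says that people above 3 × ULN "should be monitored more frequently to determine if they are" adapting or susceptible, and that suspected cases return "preferably within 48 hours from awareness of the abnormal results".

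**Conclusion.** The ECG point holds and is minor. The SAP's 500 ms row does not measure the protocol's 500 ms threshold except at 60 bpm, so the incidence by arm at that threshold is not tabulated. This rests on two assumptions: that QTc in Protocol 9.9.3 means QTcF, which the read list supports, and that the standard Fridericia formula is used. It would be wrong to infer that QTcF values above 500 ms would go unseen, since other rows and the listings show them.

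The liver point is secondary and optional. The plot can misplace a case, but the combined row counts the usual one, and only the course Appendix 6 calls rare may escape the by-visit row. The documents give no frequency for either situation, and none is claimed. The primary analysis, sample size and error control are untouched.

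**What to change.** **ECG.** Add QTcF above 500 ms to the absolute criteria in SAP 6.3.2.2, beside or in place of the QT row. The cost is one table row from data already collected.

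**Liver, optional.** State whether the overall post-baseline combined row needs both values in one sample. The sponsor may also keep the same-day plots and add a version using the peak bilirubin on or after the date of the enzyme peak, within a window fixed before unblinding. That version should say whether local repeat results count, because SAP 6.3.2.1 generally keeps local results out of summaries. A wide window has a drawback, since Appendix 6 says: "Rises in AST/ALT and total bilirubin separated by more than a few weeks should be assessed individually based on clinical judgment". The cost is one sentence, a little programming and perhaps a few extra points to review individually. No clinical rule changes.
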